	The main estimand for the primary efficacy endpoint is defined as a binary variable indicating disease progression (death or respiratory failure) at Day 14. Intercurrent events that lead to study drug discontinuation and/or switch to other treatment before Day 14 will be handled using the treatment-policy strategy (ie, the NIAID score at Day 14 will be used for definition of the failure in such patients). Missing data on Day 14 resulting from study termination before Day 14 are not expected. However, in case they happen, such monotone missings will be imputed by multiple imputation using information from similar patients of the same treatment group. Missing post-baseline data for patients randomized but not treated will be imputed by the respective baseline value (baseline observation carried forward, BOCF). The comparison between the treatment groups considering all randomized patients after having imputed missing values will be performed using Mantel-Haenszel (MH) test for risk difference considering the 4

This document is confidential.

Page 14 of 85

MetrioPharm AC	j
MP1032	

MP1032-CT05 Protocol v2.0

strata resulting from the 2 randomization stratification factors disease severity
(moderate versus severe) and age-class (aged ≤65 years versus >65 years) at baseline.
Similar MH analyses will be conducted for the main estimand of the first key secondary efficacy endpoint, which is defined as a binary variable indicating disease progression (death or respiratory failure) at Day 28, and the main estimand for the second key secondary efficacy endpoint, which is defined as a binary variable indicating disease resolution (alive and have a score of 6, 7 or 8 on NIAID) at Day 28. Intercurrent events that lead to study drug discontinuation and/or switch to other treatment before Day 28 will be handled using the treatment-policy strategy for these estimands (ie, the NIAID score at Day 28 will be used for definition of the failure or response, respectively) in such patients. Missing data on Day 28 will be imputed by multiple imputation using information from similar patients of the same treatment group.

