15 STATISTICAL ANALYSIS

The statistical analysis plan (SAP) will provide further details regarding the definition of analysis variables and analysis methodology to address all study objectives. The SAP will be finalized before any statistical output (eg, DSMB output) is produced. The SAP will serve as a companion document to the protocol. The SAP will further describe the statistical analyses. All data will be included with the final CSR.

The statistical evaluation will be performed using $SAS^{(R)}$ software version 9.4 or higher (CCI \square).

Summary statistics will be presented by treatment group. Continuous and ordinal variables will be summarized by the number of patients (N), mean, standard deviation, median, minimum, and maximum for actual values and change from baseline. Additionally, for ordinal data, the number and percentage of patients in each category will be presented. Binary and categorical variables will be summarized for each treatment group by presenting the number and percentage of patients in the categories.

Statistical tests for comparison between treatments will be performed using a two-sided alpha level of 10%. No adjustment for multiple testing will be applied in this descriptive proof-of-concept study.

151 Determination of Sample Size

The primary efficacy endpoint "proportion of patients with disease progression on Day 14" is assumed to be 10% in the 300 mg MP1032 BID plus SoC treatment group (Arm A) and 30% in the placebo plus SoC treatment group (Arm B). Using the Chi-square test with type I error alpha=10% two-sided for this proof-of-concept study and 2:1 randomization ratio, with 114 randomized patients (76 in Arm A and 38 in Arm B) a statistical power of 83% can be achieved. Considering about 5% early study terminations, the necessary sample size to randomize results is 120 patients in total (80 in Arm A and 40 in Arm B). If during the conduct of the study the early study termination rate is higher than the estimated 5%, then an increase in the randomized number of patients may be necessary.

Sample size estimation was performed using nQuery 8, Version 8.6.1.0.

A subset of randomized patients will be consented for the collection of blood samples for PK measurements. The PK subset consists of approximately 20 patients from the 300 mg MP1032 BID plus SoC group and approximately 10 patients from the placebo plus SoC group, up to a total of approximately 30 patients.

This document is confidential.

Page 69 of 85

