Missing data on Day 14 resulting from study termination before Day 14 are not expected. However, in case they happen, such monotone missings will be imputed by multiple imputation using information from similar patients of the same treatment group. Missing postbaseline data for patients randomized but not treated will be imputed by the respective baseline value (baseline observation carried forward [BOCF]). The comparison between the treatment groups will be performed on the ITT after imputation of missing values using MH test for common risk difference considering the 4 strata resulting from the 2 randomization stratification factors disease severity (moderate versus severe) and age-class (aged ≤ 65 years versus > 65 years). The 95% confidence intervals will be provided for the risk difference.

Similar MH analyses and presentation of 95% confidence intervals will be applied to the main estimand of the first key secondary efficacy endpoint, which is defined as a binary variable indicating disease progression (death or respiratory failure) at Day 28, and the main estimand of the second key secondary efficacy endpoint that is defined as a binary variable indicating disease resolution (alive and have a score of 6, 7 or 8 on NIAID) at Day 28. Intercurrent events that lead to study drug discontinuation and/or switch to other treatment before Day 28 will be handled using the treatment-policy strategy for these 2 estimands (ie, the NIAID score at Day 28 will be used for definition of the failure or response, respectively) in such patients. Missing data on Day 28 will be imputed by multiple imputation using information from similar patients of the same treatment group. Missing postbaseline data for patients randomized but not treated will be imputed by BOCF.

A similar MH approach and presentation of 95% confidence intervals as described above will be applied also to the main estimand of the third key secondary efficacy endpoint, which is the all-cause mortality at Day 28. Intercurrent events that lead to study drug discontinuation and/or

This document is confidential.

Page 71 of 85
switch to other treatment before Day 28 will be handled using the treatment-policy strategy (ie, the life status at Day 28 will be considered). No missing data of life status on Day 28 is expected.

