The main estimand of the fourth key secondary efficacy endpoint, change of clinical status related to COVID-19 on Day 28 compared with baseline according to the NIAID 8-point ordinal scale, will be compared using the risk difference from the analysis of covariance model with treatment and the 2 binary stratification factors (eg, severity and age-class) as independent factors and the baseline value of NIAID as independent covariate. Intercurrent events that lead to study drug discontinuation and/or switch to other treatment before Day 28 will be handled using the treatment-policy strategy for this estimand (ie, the NIAID score at Day 28 will be used). Missing data on Day 28 will be imputed by multiple imputation using information from similar patients of the same treatment group. Missing post-baseline data for patients randomized but not treated will be imputed by BOCF. The 95% confidence intervals will be provided for the risk difference.

The population for all above described estimands of the key secondary endpoints is the ITT.

Sensitivity analyses for the main estimands of the primary and key efficacy endpoints will be performed by assuming missing data at Day 14 or Day 28 as failure or non-resolution for the binary endpoints, and by multiple imputation using information from similar patients of the placebo group for the NIAID 8-point ordinal scale.

All above analyses for the main estimands of the primary efficacy and key secondary efficacy endpoints will be repeated on PPS as supportive analysis. Additionally, for the primary efficacy and binary key secondary efficacy endpoints, logistic regression model with treatment and the 2 stratification factors as covariables will be performed on the ITT. Further estimands for the primary and key secondary efficacy endpoints will be provided in the SAP.

The proportion of patients with disease resolution at Day 14 and the all-cause mortality rate at Day 14 and Day 60 will be analyzed using similar MH methods as described above for Day 28. Cumulative proportion of patients with disease resolution will be plotted by time.

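### Carrying baseline forward for untreated patients with missing data sets their outcome by entry oxygen status; placebo-based multiple imputation fits the estimand better

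*Protocol*

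**What the plan says.** Section 15.3 of the protocol uses two methods for missing outcomes in the main analyses. Patients who leave the study early are multiply imputed from similar patients in their own arm. Patients who were randomized but never dosed are handled separately. For the primary endpoint: "Missing postbaseline data for patients randomized but not treated will be imputed by the respective baseline value". The rule is repeated for Day 28 progression and Day 28 resolution, and for the change in NIAID score: "Missing post-baseline data for patients randomized but not treated will be imputed by BOCF". The Synopsis gives it for the primary endpoint: "Missing post-baseline data for patients randomized but not treated will be imputed by the respective baseline value".

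The primary event is death or an NIAID score of 2, 3 or 4 (Sections 6.2 and 15.3). Score 4 is a hospitalized patient on supplemental oxygen. Score 5 is a hospitalized patient who needs care but no oxygen. Resolution is a score of 6, 7 or 8. Study drug discontinuation and a switch of treatment are handled by a treatment-policy strategy.

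Section 15.3 also plans sensitivity analyses. Missing counts as failure or non-resolution for the binary endpoints, and the NIAID scale is imputed from similar placebo patients. The primary and key secondary analyses are repeated on the Per Protocol Set, which requires at least one dose (Section 15.2).

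**The concern.** Sections 8.1 and 8.2 admit hospitalized patients with moderate or severe disease and exclude critical disease. A patient on low-flow oxygen can therefore enter at score 4, which already meets the definition of the primary event. Carrying that score forward records disease progression in someone about whom nothing is known after entry. A patient entering at score 5 is recorded as event-free on equally little information. For Day 28 resolution, everyone entering at score 5 or below is recorded as unresolved. For the NIAID scale, the change is exactly zero.

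An untreated patient still receives standard of care, so under a treatment-policy estimand the outcome wanted is the one under standard of care. Assuming no change over 14 or 28 days is a poor stand-in for it. With only 40 patients planned in Arm B, a few such patients, unevenly split by chance, could move the estimate according to their entry score rather than their outcome. A single imputed value also brings no imputation uncertainty, unlike the multiple imputation used for the other missing outcomes.

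**Working it through.** **Inputs.** From Section 15.1: the Day 14 progression rate "is assumed to be 10% in the 300 mg MP1032 BID plus SoC treatment group" and 30% in the placebo arm. The test is fixed as "Using the Chi-square test with type I error alpha=10% two-sided". Also "with 114 randomized patients (76 in Arm A and 38 in Arm B) a statistical power of 83% can be achieved", and 120 randomized (80:40) after about 5% early terminations. Not in the protocol, so assumed here: u, the share of an arm that is untreated with missing data; q, the share of those patients entering at score 4 or lower; and a 30% risk under standard of care for untreated patients in either arm.

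**The plan's own figure.** A pooled-variance chi-square test without continuity correction, with 76 at 10% and 38 at 30%, has power 0.830, matching the stated 83%. 114/0.95 = 120, as stated. With 80:40 and nobody untreated, power is 0.846.

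**Does the rule conflict with 10% and 30%?** Under carry-forward the imputed event probability is 1 at score 4 or lower and 0 at score 5 or higher, so these patients' average imputed rate is q. It equals the 30% standard-of-care rate only if q = 30%; at q = 50% or 90% it is 50% or 90%. The protocol does not give q.

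**Shift per patient, against a 30% risk.**
- Score 4 in Arm A: (1 - 0.30)/80 = 0.875 points, making the difference less favorable to MP1032.
- Score 4 in Arm B: (1 - 0.30)/40 = 1.75 points, making it more favorable.
- Score 5: 0.30/80 = 0.375 points (Arm A) or 0.30/40 = 0.75 points (Arm B), in the opposite directions.

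**Two illustrative splits, all entering at score 4.**
- Three in A, one in B, carried forward: A = (77 × 0.10 + 3)/80 = 13.375%; B = (39 × 0.30 + 1)/40 = 31.75%; difference -18.4 points. At the standard-of-care rate: A = (77 × 0.10 + 3 × 0.30)/80 = 10.75%; B = 30%; difference -19.25 points. The gap is about 0.9 points.
- None in A, two in B, carried forward: B = (38 × 0.30 + 2)/40 = 33.5%; difference -23.5 points, against -20.0 points at the standard-of-care rate. If both had entered at score 5, B = (38 × 0.30)/40 = 28.5% and the difference would be -18.5 points.

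**Equal untreated shares and the same entry mix.** Carried forward: [(1 - u) × 0.10 + uq] - [(1 - u) × 0.30 + uq] = -0.20(1 - u), whatever q is. Standard-of-care rate: [(1 - u) × 0.10 + u × 0.30] - 0.30 = -0.20(1 - u). The differences are identical. At u = 5% both are -19.0 points. Power at 80:40 is then 0.806 with the standard-of-care rate, and 0.806, 0.793, 0.781 and 0.769 with carry-forward at q = 30%, 50%, 70% and 90%.

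**Do the planned checks test the rule?** Counting missing as failure changes untreated patients who entered at score 5 or higher. Those at score 4 are failures either way. For Day 28 resolution the two methods agree for everyone entering at score 5 or below.

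**The case against.** A reader might infer that the rule contradicts the planned rates. It does not: 10% and 30% are arm averages, and a mix of certain events and certain non-events can average 30%. Nor do 70% event-free patients prove recovery from score 4, because someone who enters and stays at score 5 is also event-free.

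The scope is narrow. Only missing data of never-dosed patients are affected; observed Day 14 and Day 28 scores are used. Randomization and first dose are both scheduled for Day 1 in hospital, so few such patients are likely, and the double blind makes a systematic imbalance between arms unlikely. A reader might also measure the Arm A shift against 10%, giving (1 - 0.10)/80 = 1.125 points. That credits a drug effect to patients who took no drug; 0.875 points is the consistent figure.

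A further tempting inference is that the confidence interval is shown to be too narrow. It is not: no interval was computed, and in the three-and-one split the simple unstratified standard error rises from about 0.080 to 0.083. The missing imputation uncertainty is a point of principle whose size is unknown.

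A separate rule for untreated patients is also sensible, since same-arm imputation would give untreated Arm A patients the drug effect. The Per Protocol repeat excludes all of them.

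All of this limits the size of the problem. What remains is that carry-forward is an implausible form for that separate rule, that counting missing as failure leaves score-4 patients untouched, and that the Per Protocol repeat also drops patients with major deviations, so it does not isolate the rule.

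**Conclusion.** The point holds as a weakness in a rule the protocol itself fixes, not as an internal contradiction. For untreated patients with missing data, the main analyses replace the outcome under standard of care with entry status. Scores 4 and 5 are the usual entry cases. Score 3 (high-flow oxygen below the threshold for critical disease) and score 6 are not formally excluded, and follow the same logic.

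The size rests on assumptions: a 30% risk under standard of care, and a number untreated and an entry mix that the protocol does not give. On that footing each score-4 patient moves the risk difference by about 0.9 points in Arm A or 1.75 points in Arm B. The illustrative splits give gaps of 0.9 and 3.5 points. Bias can go either way and, at the planning rates, vanishes from the difference when untreated shares and entry mix match across arms. The practical effect is probably small. The change is worth making because the better method is already in the plan.

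**What to change.** In Section 15.3 and the Synopsis, replace baseline carried forward in the main estimands. For randomized-but-untreated patients with missing Day 14 or Day 28 data, in either arm, use multiple imputation from placebo-plus-standard-of-care patients with similar randomization stratum and baseline NIAID score. This extends the placebo-based imputation already planned as a sensitivity analysis for the NIAID scale. Because 40 placebo patients over four strata average only 10 per stratum, use a regression-type imputation model rather than matching within cells. Keep baseline carried forward as a sensitivity analysis; comparing it with the main result then varies the score-4 patients, which counting missing as failure does not. Report the number of such patients by arm and entry score. Align the country versions; the Bulgarian Synopsis carries the same rule.

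The cost is a wording change and slightly more imputation work, for what is probably a handful of patients.

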5 INTRODUCTION

51 Background on COVID49

On 31 December 2019, the World Health Organization (WHO) was informed of a cluster of cases of pneumonia of unknown cause detected in CCI . Severe acute respiratory syndrome coronavirus type 2 (SARS-CoV-2) was identified as the causative virus by Chinese authorities on 07 January 2020 (WHO 2020a). Coronavirus disease 2019 (COVID-19) was identified as the disease caused by SARS-CoV-2 infection. In March 2020, the COVID-19 outbreak was declared as a pandemic by the WHO. The disease resulting from SARS-CoV-2 led to shutdowns and social measures in great parts of the world, particularly to slow down the transmission of the virus and thereby avoiding the overburden of health care systems.

The pandemic is still ongoing. Estimates of actual morbidity, mortality, and lethality are highly variable and depend on factors such as the time of analysis, region analyzed, and surveillance methods. As of 04 August 2020, the WHO estimated the case fatality ratio, which estimates the proportion of deaths among confirmed cases, to vary from 0.1% to >25%. Whereas, the true severity of COVID-19 as measured by the infection fatality ratio, which estimates the proportion of deaths among all infected individuals, is estimated to be approximately 0.5% to 1% (WHO 2020b). In a more recent summary of Levin et al (2020) it could be clearly shown that the infection fatality ratio is highly age dependent, being in average as low as 0.004% for patients younger than 35 and as high as 28.3% in patients at the age of 85 and older.

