A similar analysis of covariance approach as described above for Day 28 will be applied for the analysis of the change of clinical status related to COVID-19 on Day 14 compared with baseline on the NIAID 8-point ordinal scale. The endpoint considering the proportion of patients requiring invasive ventilation (mechanical ventilator and/or ECMO) or who are not alive, the proportion of patients in each NIAID category, and the proportion of patients alive and testing negative for COVID-19 on Day 14, Day 28, and Day 60, respectively, will be compared between the treatment groups using MH test. Overall survival, time to (first) improvement of at least 1 category on the NIAID scale and total hospitalization duration (from baseline to discharge; with death censored on last day of the observed period – at Day 28 or Day 60, respectively – depending on the analyses) will be summarized using the Kaplan-Meier method and will be compared between treatment groups using log-rank tests. Additionally, Cox proportional hazards model will be applied with treatment and the 2 stratification factors as covariables.

This document is confidential.

Page 72 of 85

Final

MetrioPharm AG MP1032	MP1032-CT05	
	Final	
MetrioPharm AG	MP1032-CT05	
MP1032	Protocol v2 0	

The odds ratio between MP1032 and SoC and placebo and SoC for the number of patients with clinical status improvement from baseline on the NIAID 8-point ordinal scale (ie, an improvement of at least 1 category) at Day 14 and Day 28 will be analyzed using a logistic regression with consideration of the 2 stratification factors.

The time to recovery of all at baseline present COVID-19 symptoms (stuffy or runny nose, sore throat, red or irritated eyes, shortness of breath, cough, low energy or tiredness, muscle or body aches, headache, chills or shivering, feeling hot or feverish, nausea, and number of times of vomit, times of diarrhea, sense of smell, sense of taste in the last 24 hours) will be presented by Kaplan-Meier estimates and figure. The change from baseline will be presented in shift tables for each single symptom, with the number and percentage of subjects in each category at post-baseline assessment time-point compared to baseline for each treatment group.

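### The ANCOVA of change in NIAID score uses age only as the randomization class (≤65 v >65); adding age in years beside the class would recover a little precision at the cost of one degree of freedom

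*Protocol*

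**What the plan says.** Protocol section 15.3 (Efficacy Analysis) names the covariates of each regression model.

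- **Change in NIAID score at Day 28 (fourth key secondary endpoint, main analysis):** "analysis of covariance model with treatment and the 2 binary stratification factors (eg, severity and age-class) as independent factors", plus baseline NIAID. A similar ANCOVA is applied at Day 14.
- **Primary and binary key secondary endpoints, additional analysis:** "logistic regression model with treatment and the 2 stratification factors as covariables will be performed on the ITT". The odds ratio for improvement by at least one category also comes from a logistic regression with the two stratification factors.
- **Time-to-event endpoints, in addition to the log-rank test:** "Cox proportional hazards model will be applied with treatment and the 2 stratification factors as covariables".

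Age-class (≤65 v >65) is one of the two randomization factors (section 9.3.1). Age is recorded as a demographic variable (section 12.1 and footnote f of Table 1). Entry is open to adults from 18 years with no upper limit (section 8.1). Section 5.1 says that the "infection fatality ratio is highly age dependent, being in average as low as 0.004% for patients younger than 35", rising to 28.3% at 85 and older, and that the elderly seem more vulnerable to a severe course. Age in years appears in no efficacy model in section 15.3.

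**The concern.** A single cut at 65 gives a 25-year-old and a 65-year-old the same covariate value, and likewise a 66-year-old and a 90-year-old. If outcome worsens steadily with age, the part of that trend lying within each class stays in the residual of the ANCOVA. With about 80 v 40 patients, chance age differences between arms within a class then add noise to the treatment effect. Stratified randomization and the class term deal with imbalance between the classes, but not within them.

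At stake is some precision in the main analysis of one key secondary endpoint and in its Day 14 counterpart. The variable is already collected, and naming it before unblinding avoids the appearance of a data-driven choice later.

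**Working it through.** **1. The plan's own figure.** Section 15.1 states that "with 114 randomized patients (76 in Arm A and 38 in Arm B) a statistical power of 83% can be achieved", for 10% v 30% with a two-sided 10% chi-square test.
- Pooled rate: (76 × 0.10 + 38 × 0.30)/114 = 0.1667.
- SE under the null: √(0.1667 × 0.8333 × (1/76 + 1/38)) = 0.0740.
- SE under the alternative: √(0.09/76 + 0.21/38) = 0.0819.
- Power: Φ((0.20 − 1.645 × 0.0740)/0.0819) = Φ(0.955) = 0.830.
- 114/0.95 = 120.

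Both figures reproduce. They rest on an unadjusted test and do not depend on how age is modelled.

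**2. How much of a linear age effect the class keeps.** The inputs are assumptions, since the documents give none: age normal, mean 50-70, SD 12-15. With c = (65 − mean)/SD, p = 1 − Φ(c) and φ the normal density, the share kept is φ(c)²/(p(1 − p)).
- Mean 60, SD 15: c = 0.333, φ = 0.377, p = 0.369; share = 0.1424/0.2330 = 0.61.
- Lowest in the range (mean 50, SD 12): c = 1.25, φ = 0.183, p = 0.106; share = 0.35.
- Highest (mean 65): c = 0, φ = 0.399, p = 0.5; share = 0.1592/0.25 = 0.64.

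**3. Variance inflation of the ANCOVA treatment effect.** Let R² be the share of outcome variance explained by age, given the other covariates (assumed 2-20%). Inflation from using the class instead of age in years is (1 − share × R²)/(1 − R²). Equivalent patients are 120 × (inflation − 1).

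| Age R² | Share 0.64 | Share 0.61 | Share 0.35 | Patients of 120 |
|---|---|---|---|---|
| 2% | 1.007 | 1.008 | 1.013 | 1-2 |
| 10% | 1.040 | 1.043 | 1.072 | 5-9 |
| 20% | 1.091 | 1.097 | 1.162 | 11-19 |

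**4. Simulation of the recommended form (class and age together).** Settings: 120 patients, 2:1 within the four strata, mean age 60, SD 14, true effect 0.5 SD, two-sided 10%, severity in the model, 4,000 runs.

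| Age R² | SE, class | SE, class + age | Variance ratio | Power, class | Power, class + age |
|---|---|---|---|---|---|
| 2% | 0.1921 | 0.1922 | 1.00 | 83.1% | 82.8% |
| 10% | 0.1875 | 0.1844 | 1.03 | 83.9% | 84.8% |
| 20% | 0.1809 | 0.1735 | 1.09 | 86.8% | 89.2% |

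The Monte Carlo error of each power figure is about √(0.84 × 0.16/4000) = 0.6 points, so the 2% row shows no difference. Replacing the class by age gives almost the same SE as adding age (0.1839 v 0.1844 at R² 10%).

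A separate proportional-odds simulation of the 8-category Day 28 score assumed age about N(60, 15) and slopes of 0.02 to 0.10 log-odds per year. With age in place of the class, its variance ratios were 1.01 to 1.12. Power went from 74.2% to 74.4% at the shallowest slope, from 74.9% to 74.7% at 0.04 and from 66.1% to 69.3% at the steepest.

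**5. Logistic and Cox models.**
- Logistic (N = 114, age in years instead of class): power went from 85.5% to 86.0%, 83.3% to 84.3% and 86.6% to 87.6% at age odds ratios of 1.3, 1.6 and 2.0 per 10 years. The SE of the log odds ratio rose (0.579 to 0.590 at 1.6). A second set of assumptions gave gains of up to 1.6 points (88.1% to 89.7%).
- Cox (300 runs, age added to class): SE 0.224 v 0.226, 0.225 v 0.227 and 0.227 v 0.229 at age hazard ratios of 1.0, 0.85 and 0.7 per 10 years; power 67.0% v 66.3%, 64.7% v 63.0% and 59.0% v 61.0%. Monte Carlo error is about √(0.6 × 0.4/300) = 2.8 points, so no gain can be distinguished from zero.

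**The case against.** The strongest reply is that nothing here is wrong. Age-class is a randomization factor, the Mantel-Haenszel analyses use the same strata, and adjusting the models for the factors used in randomization is coherent. That stands, and it is why the class should stay. The benefit is also small, rests on assumptions the documents cannot confirm, and was tested where a linear term suits the data. If risk simply stepped up at 65, the class would capture it all and age in years would only cost its degree of freedom. That stands too.

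Four stronger readings are tempting, and the documents do not support them.

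- A reader might infer that the class wastes precision to no purpose and should be replaced. It reflects the randomization, and adding age beside it performs almost as well as replacing it.
- A reader might infer wider intervals in the logistic and Cox models too. In the logistic model the SE rises slightly with age in years, and in Cox no gain is visible.
- A reader might take the fatality gradient in section 5.1 as the effect size. It concerns all infected people. The ANCOVA concerns NIAID status in hospitalized adults without critical disease and already adjusts for severity and baseline NIAID. The gradient supports the direction, not the R².
- A reader might infer that the primary result is affected. The primary and the three binary key secondary endpoints use stratified Mantel-Haenszel.

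The statistical analysis plan is not at hand and may add sensitivity models with further covariates. The protocol, however, already names the covariates of the main ANCOVA, so the suggestion is not merely a request for detail left to that plan.

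**Conclusion.** The point holds as an optional improvement to the ANCOVA of change in NIAID score at Day 28 and Day 14. Using the class alone costs about 1% in variance if age explains little (R² 2%), 4-7% at R² 10% and 9-16% at R² 20%, with a power difference of about 0-3 points. At the low end, adding age beside the class gains nothing measurable and loses nothing measurable.

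The size depends on an assumed mean age of 50-70, an SD of 12-15, a roughly linear age effect, and the R² left after severity and baseline NIAID, none of which the documents give. The middle of the range, 5-9 patients, is comparable with the 6 patients (120 − 114) added for early terminations. Logistic power would gain about 0-1.6 points without a smaller standard error, and for Cox no gain is shown.

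**What to change.** In section 15.3 and the synopsis, keep severity, age-class and baseline NIAID in the ANCOVA and add age in years as a linear covariate, for Day 28 and Day 14 alike. Make the change before unblinding. Leave the Mantel-Haenszel analyses and their four strata unchanged. If the same covariate is added to the logistic and Cox models, give consistency as the reason and claim no narrower intervals.

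The cost is one phrase in each place, including the Bulgarian version, whose synopsis repeats the text, and one degree of freedom in the model. No new data are needed, and the sample size does not change.
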